v2.1, dd 24Nov2021

## **RESEARCH PROTOCOL SUMMARY**

TITLE:	PEDAL; Plantar Exercise, Daily, for Lymphoedema, a single- centre, controlled, prospective, randomized feasibility trial			
Short title:	PEDAL trial			
IRAS number	265968			
Device description Study design	StepIt plantar flexion rocker pedal device. CE-marked and licensed medical device. To be used in this study for indicated purpose, namely plantar flexion exercise.Multi centre, controlled, prospective randomized feasibility			
	trial			
Primary objective	To assess the feasibility of conducting a full RCT in the future			
	
 
Participants' compliance to StepIt exercise regime and total number of steps achieved
 
Recruitment and attrition rates, willingness of patients to be randomised, response rates to questionnaires, and degrees of missing data
 
Testing of eligibility criteria and ability/willingness of clinical staff to partake in recruitment of participants
 
Adequacy of duration of follow-up (e.g. in relation to lymphoedema status)
 
			
Secondary objectives	To determine the acceptability and efficacy of the step-it pedal as an adjuvant therapy for leg lymphoedema at 6 and 12 weeks post-baseline			
	
 
Efficacy of StepIt pedal adjunct therapy vs standard care. Status leg volume difference.
 
Ankle circumference
 
Ankle range of motion
 
Lymphoedema-related quality of life
 
General quality of life
 
Patient feedback on use of the device (StepIt users only)
 
			
Patient population	A total of 24 participants, over the age of eighteen, with leg lymphoedema managed by the community lymphoedema team. Participants must have the capacity to provide informed written consent and complete patient reported outcome measures. Participants are recruited from the local Hospice at Home lymphoedema service caseload.			

	
 
12 Patient will receive treatment as usual (TaU)
 
12 Patients will receive TaU plus StepIt exercise programme intervention
 
			
	Randomisation will not be stratified.			
Sponsor	North Cumbria Integrated Care NHS Foundation Trust			
Manufacturer & funder	StepIt System AB, [name] Contact: [name], PhD, [contact]			
	[contact]			
Chief Investigator	[name], GPwSI Research, North Cumbria Integrated Care NHS Foundation Trust, R&D Department, [name] [contact]			
Co-investigators				

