Currently, chronic lymphoedema can be managed but not cured. The mainstay of interventions includes decongestive lymphatic therapy (DLT), which consists of manual lymphatic drainage (MLD), a specialised medical massage to soften and drain lymph fluid, and compressive bandaging. Patient compliance with treatments is paramount for their success. Patients are also advised to take regular exercise to control the lymphoedema symptoms. The latter proves a challenge in leg lymphoedema patients because of the morbidity associated with their condition (Bogan et al, 2007). This brings about the risk of a vicious circle where less exercise leads to further worsening of lymphoedema symptoms. Whilst exercise could be of particular benefit for this group of patients' research suggests that around 50% of sedentary adults who start an exercise programme stop within the first 6 months of involvement (Heinen *et al* 2007). Patients may be receptive to this form of exercise especially if they are elderly, frail, have limited mobility, have a fear of falling or are housebound.

This study will apply a StepIt rocker pedal for the first time in patients with leg lymphoedema in addition to the standard care. This is a small pedal device that can be used from a seated position and was first devised to help alleviate the risk of deep vein thrombosis for travellers on long haul flights; a reduction in swelling was demonstrated in people who sat in a sedentary position for lengthy periods (Bergqvist, 2009). Subsequently, the StepIt device has been trialled in a clinic setting in patients with peripheral arterial disease (PAD) and venous leg ulcers, respectively (Tebbutt et al, 2013; Jonker et al, 2019). In the study by Tebbutt et al, encouraging results were obtained - in terms of increase in maximum walking distance for PAD patients who used the StepIt pedal – when a 20-minute exercise regime was prescribed. Jonker et al showed a trend towards improved healing rates of VLUs with the same exercise regime as for PAD patients. The StepIt pedal specifically exercises the calf muscle by performing plantar flexion exercise.

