#### 4.2 Secondary objective

• To assess the acceptability and efficacy of the Step-It pedal as an adjuvant therapy for lymphoedema symptom control.

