#### 5.2 **Participant identification & consent**

Patients with leg lymphoedema will be screened for eligibility for this study by the Chief Investigator. All eligible patients will be invited to take part until the required numbers have been achieved. Patients will be recruited sequentially and randomised into two groups: one control group receiving care as usual and one intervention group receiving care with the StepIt device. The eligible patient population is defined in the Inclusion and Exclusion criteria section. A delegated member of the research team will join the (non-research) lymphoedema care specialist to the first appointment provided the patient has consented to this verbally. During this visit /clinic appointment the study will be discussed in further detail and the participant has the opportunity to ask questions that they may have. If potential participants meet the eligibility criteria, the patients can be consented by the Clinical Lymphoedema Specialists or Research Nurses/Practitioners , the latter as long as the patient's verbal consent has been sought from the treating clinical staff. A screening form will be completed for potentially eligible patients to confirm that they indeed meet the trial criteria.

During the screening visit all patients get the opportunity to try out the Step-It pedal. This also functions as a screening tool, since those patients who cannot perform the required ankle/foot movements cannot enter the trial. Significant discomfort will also be a reason for exclusion. The outcomes of this screening exercise will be recorded in the screening log.

Patients will be given > 24 hrs to consider if they wish to take part, and can ask questions regarding the study. If they understand the nature of the study and are happy to take part, written informed consent will be obtained.

Participants will receive no incentives and consent will be regarded as a process and not a one off event. Participants are free to withdraw from the study at any time without the need to give any reasons for withdrawal. Their standard care will not be affected by either declining to participate in the study or withdrawing during participation.

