#### 5.3 Recruitment

Participants will be randomised to either the control group (standard care) or the intervention group (standard care plus use of a StepIt pedal) for 12 weeks. Patients in both groups will be given the usual lymphoedema management information, but those in the intervention group will be issued with a StepIt Pedal to use daily for foot and ankle exercises. The participants will be asked to report on their activity at the end of trial (self-reported compliance Likert scale question). At their discharge visits participants are also asked to provide their wider opinion on trial participation. All participants will have demographic data obtained and the following base line measures (Table 3):

T	able	3.	Baseline	measures
•	abic	٠.	Duschine	measures

Weeks	0	6#	12#
Leg volume	Х	Х	Х
Ankle circumference	Х	Х	Х
Ankle range of motion	Х		Х
Visual analogue pain score	Х	Х	Х
LYMQOL-Leg	Х	Х	Х
EQ-5D-5L	Х	Х	Х
PEDAL experience questionnaire			Х

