#### 5.5.2 Secondary outcome measures

The primary outcome for this pilot trial will be the feasibility of conducting a full RCT in the future. However, this study also aims to provide preliminary results regarding the acceptability and efficacy of a simple StepIt pedal as an adjuvant therapy for lymphoedema symptom control.

Clinical outcome measures

- Leg volume (see notes below), at week 0, 6, 12
  - Measured only between 9.30am to 3.30pm
  - Where possible the same rater is used for each participant; name of rater will be recorded.
- Ankle circumference measurement, using lateral malleolus as reference point (Brodovicz et al, 2009), at week 0, 6, 12
- Clinician's oedema severity score (Table 4 below; Nieman et al, 2013)

Table 4.	Clinician's	oedema	severity	/ score
TUDIC T,	chinciun 5	ocucina	JUVUII	, 20010

	0	1+	2+	3+	4+
Visible	No	yes	yes	yes	yes
Pitting	No	slight	>slight	>slight	'can't reach tibia'
Level	n/a	n/a	< knee	>knee	>knee

- Ankle range of motion (using goniometer)
- Pain score, at week 0, 6, 12
- Quality of life score, determined with EQ-5D-5L and LYMQOL-L Questionnaire, at week 0, 6, 12
- Participant opinion on trial participation, at week 12 (StepIt users only)
- Patient withdrawal rates due to change in management (e.g. need for surgery, hospital admission, infection, or other)
- Leg infection rates, primarily cellulitis

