#### 6.3 Early withdrawal of subjects + intervention suspension

Patients have the right to withdraw from the trial at any time and without giving any reason. If a patient withdraws from the trial, any and all information gathered prior to the withdrawal will be included in the analysis, but no further data collection will occur. If a patient does not attend a planned follow-up appointment then two more attempts will be made to contact the patient regarding the study. If still no contact can be made then the patient is deemed lost to follow-up and any collected study data will be retained.

If a patient needs to suspend the StepIt exercises then this does not change the planned follow-up dates for 6 and 12 weeks after baseline study visit. This may be eg hospital admission. If a patient develops an infection then the routine approach will be: rest of the legs (ie no StepIt exercises) for duration of antibiotics course + 1 week. Intervention suspension events will be recorded.

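### The summary promises acceptability and efficacy at week 6, but the experience questionnaire and ankle range of motion are not collected then, and StepIt users who leave before their final visit are never asked their opinion of the pedal

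*Protocol*

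**What the plan says.** The Protocol summary states the secondary objective as "To determine the acceptability and efficacy of the step-it pedal as an adjuvant therapy for leg lymphoedema at 6 and 12 weeks post-baseline". The measures listed under it include ankle range of motion and "Patient feedback on use of the device (StepIt users only"). Section 4.2 gives the same objective without time points: "To assess the acceptability and efficacy of the Step-It pedal as an adjuvant therapy for lymphoedema symptom control".

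Table 3 in section 5.3 marks the "PEDAL experience questionnaire" at week 12 only. It marks ankle range of motion at weeks 0 and 12, with week 6 blank. Section 5.5.2 agrees on the timing of the opinion item: "Participant opinion on trial participation, at week 12 (StepIt users only"). Section 8.3 analyses ankle range of motion as the difference between the first and last visits.

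On people who leave, section 6.3 says that "any and all information gathered prior to the withdrawal will be included in the analysis, but no further data collection will occur". A participant who misses a visit and cannot be reached after two further attempts is treated as lost to follow-up. Sections 5.2 and 6.3 both allow withdrawal without a reason.

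**The concern.** An objective stated at two time points needs data at both. Two of the measures listed under this one have no week-6 data, and no analysis plan can supply what the schedule does not collect.

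The second problem is who answers. Acceptability is in the research question (section 2.1) and the secondary objective, and in a 24-person feasibility trial it bears directly on whether a full trial should follow. The only instrument that asks StepIt users for their opinion comes at the end. Someone who leaves early because the pedal does not suit them is a likely source of an unfavourable answer, and is not asked. Opinions lost in this way cannot be recovered later.

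**Working it through.** **Step 1: objective against schedule.** Follow-up measures in Table 3 (section 5.3), checked against sections 5.5.2 and 8.3:

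| Measure | Week 6 | Week 12 |
|---|---|---|
| Leg volume | yes | yes |
| Ankle circumference | yes | yes |
| Visual analogue pain score | yes | yes |
| LYMQOL-Leg | yes | yes |
| EQ-5D-5L | yes | yes |
| Ankle range of motion | no | yes (baseline at week 0) |
| Experience questionnaire | no | yes |

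Five of the seven measures exist at week 6, and all seven at week 12. The two blank cells are not an effect of text extraction: section 5.5.2 separately puts participant opinion at week 12, and section 8.3 uses only the first and last visits for ankle motion.

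This reading takes the device feedback in the summary, the experience questionnaire in Table 3 and the participant opinion in section 5.5.2 to be one instrument. That is an assumption, since its items are not in the text at hand.

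**Step 2: who can answer the questionnaire.**
- Completes 12 weeks: asked.
- Suspends the pedal but stays in the trial: asked, because section 6.3 keeps the planned visits.
- Discharged from the service before week 12: may be asked, because section 5.3 ties the opinion question to the discharge visit. Section 5.4 expects this to be rare.
- Withdraws, or is lost to follow-up, before the final visit: not asked.

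**Step 3: how much a missing answer can matter.** Section 6.1 plans 12 StepIt users, so each non-responder is 1/12 = 8.3 percentage points of the arm. Section 6.1 also says that withdrawal rates before week 12 are not known, so a range is shown. Let d users leave unasked and k of the remaining 12 − d answer favourably. The observed proportion is k/(12 − d). Over all 12 allocated, the proportion lies between k/12 (every leaver unfavourable) and (k + d)/12 (every leaver favourable). The width is d/12.

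All counts below are assumed, with about 80% of responders favourable:

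| d | Observed | Range over all 12 |
|---|---|---|
| 0 | 10/12 = 83% | 83% |
| 2 | 8/10 = 80% | 8/12 to 10/12 = 67% to 83% |
| 3 | 7/9 = 78% | 7/12 to 10/12 = 58% to 83% |
| 4 | 6/8 = 75% | 6/12 to 10/12 = 50% to 83% |
| 6 | 5/6 = 83% | 5/12 to 11/12 = 42% to 92% |

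The observed figure barely moves while the range it conceals widens from 0 to 50 points (6/12). The protocol defines no acceptability proportion, so the table shows only how sensitive such a summary would be.

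**The case against.** **The conflict is one line of the summary.** Section 4.2 gives no time points, and Table 3 and section 8.3 agree with each other on ankle motion. This stands for ankle motion, where rewording the objective is enough. It does not help with acceptability, because the questionnaire is still given only at the end.

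**The protocol has other evidence on leavers.** It records reasons for discontinuation (section 8.2), attrition (section 6.1), suspension events (section 6.3) and pedometer counts (section 3). This stands in part. These sources show use and exit, not opinion. Reasons need not be given, and the self-reported compliance question is also asked only at the end of the trial (section 5.3).

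**An exit form may recover little.** It must be voluntary, and dissatisfied leavers may decline. That is true, but a week-6 questionnaire would still catch those who leave between weeks 6 and 12.

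A reader might also infer more than the documents support:
- *That the week-6 objective fails as a whole.* It does not: leg volume, ankle circumference, pain and both quality-of-life scales are taken then.
- *That ankle motion is measured only once.* It has a baseline; week 12 is its only follow-up.
- *That heavy loss is to be expected because* "around 50% of sedentary adults who start an exercise programme stop within the first 6 months of involvement". That figure from the introduction concerns stopping exercise, over a longer period and in a general population. Stopping the pedal is not leaving this trial, and a user who suspends it keeps the week-12 visit.
- *That the screening try-out biases the result, since* "Significant discomfort will also be a reason for exclusion". This is an eligibility rule whose outcomes go into the screening log (section 5.2). It limits whom the result describes and is not an error.

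**Conclusion.** The point holds in a limited form. The summary's week-6 objective cannot be met for acceptability by questionnaire or for ankle range of motion; it can be met for the other five scheduled measures. Separately, StepIt users who withdraw or are lost before their final visit give no questionnaire response, so the result is likely to lean favourable.

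The direction rests on the assumption that leavers think less well of the pedal than those who stay. That is plausible, but the protocol does not establish it. The size cannot be stated: withdrawal is unknown and no acceptability proportion is defined. What can be said is that each unasked user leaves about 8 percentage points of the 12-person arm undetermined. It is worth correcting because acceptability is a named objective, the remedy is cheap, and analysis cannot repair the loss.

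**What to change.** 1. In Table 3 and section 5.5.2, give the experience questionnaire to StepIt users at the existing week-6 visit as well as at week 12.
2. Offer the same questions, voluntarily, at the point of withdrawal. Section 6.3 needs a short clause allowing this, which leaves the right to withdraw without a reason untouched.
3. Report the responses together with the number allocated to StepIt and the number who did not answer.
4. In the summary, limit the ankle range of motion objective to week 12, to match Table 3 and section 8.3.

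The cost is a minor amendment and a few minutes of participant time. No new visit is needed. People who are lost to contact before week 6 will still go unasked, which is why the count of non-responders should be reported.

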#### 1. LAY SUMMARY

Chronic lymphoedema is a long-term medical condition that results in swelling of the limbs or other body parts. The cause of fluid build-up in particularly the arms and/or legs is problems with the lymphatic system, which is a network of glands and vessels that helps fight infection and remove excess liquid in the body. Lymphoedema of the legs is common in people who: may have another chronic condition such as heart failure, COPD, or vascular disease; are inactive for long periods; are overweight or obese; or have had cancer treatment to eg the pelvis. Oedema is a risk factor for serious complications such as cellulitis infection. There is some evidence to suggest that specific resistance exercise of the calf muscle – moving the front of the foot up and down by plantar flexion, similar to what a drummer does when using the foot pedal of a drum - may improve the calf muscle pump function and help reduce fluid build-up. It has been shown that at least in the short-term there is better blood flow and endurance if the calf muscle is exercised in this manner.

As yet there remains considerable uncertainty as to the effects of an exercise programme on leg lymphoedema symptom control. There is very limited research data available on the medium- to long-term effects of calf muscle exercising by lymphoedema patients on the volume of the legs. This study is a prospective, controlled, randomised, feasibility trial to determine if the use of a CEapproved plantar flexion pedal, developed by StepIt Ltd, will be of benefit to people with lymphoedema of the leg. This study initially aimed to assess the feasibility of conducting a full randomised clinical trial in the future. After analysis of results from data involving an initial 24 patients, one outcome measure will be change in leg volume at 6 and 12 weeks. Other outcome measures will include acceptability of use of the device, trial completion rates, and lymphoedemarelated quality of life. Due to the swelling experienced by leg lymphoedema patients, physical activity may be hard to achieve for some patients. Initiating calf muscle exercises whilst sitting down may be a first step in increasing physical activity for this population and improving calf muscle pump function.

#### 2. INTRODUCTION

Chronic lymphoedema is a condition where patients experience swelling of subcutaneous tissue due to insufficient drainage of interstitial fluid. The worldwide prevalence of lymphoedema is estimated to be 250 million people (Földi & Földi, 2012). The causes of lymphatic system pathology can be divided into two main types, primary and secondary lymphoedema. Primary lymphoedema is a congenital condition and occurs as a result of impaired lymph vessels or lymph node development; this can be present from birth or develop throughout life. In developed countries, secondary lymphoedema takes place as a consequence of damage to the lymphatic system due to cancer, trauma, inflammation, infection, and obesity. Lymphoedema is primarily caused by parasites in developing countries (Wynd et al ,2007). The arm is commonly affected in women after treatment for breast cancer. The leg can be affected as a result of a range of conditions, as outlined in Table 1. In homeostasis, an amount of fluid leaves the capillaries and flows into the interstitial; usually, most of this fluid is absorbed back into the blood stream and the lymphatic system pumps away the

remaining imbalance in fluid. An imbalance occurs when the microvascular (capillaries and venules) filtration rate exceeds lymph drainage over an extended period. The reasons for this may be a high filtration rate, low lymph flow or a combination of the two. The net result of this impaired drainage is a rise of proteins and solutes in the soft tissue, which can result in fibrosis and hardening of the soft tissue. The presence of oedema can have serious consequences, such as the development of cellulitis (Cox, 2006).

Cause of oedema	Associated disease state of condition
Increased capillary pressure (due to increased	Severe varicose veins
venous pressure)	
	Deep vein thrombosis
	Heart failure
Increased capillary permeability	Chronic venous insufficiency
	Allergic reaction
	Diabetes
	Drug-induced oedema
Decrease in plasma protein	Nephrotic syndomre
	Hepatic failure
Lymphatic obstruction	Filariasis or lymphatic agenesis
	Cancer treatment related oedema

Table 1, Causes of lower limb oedema (from Rabe et al, 2018)

Currently, chronic lymphoedema can be managed but not cured. The mainstay of interventions includes decongestive lymphatic therapy (DLT), which consists of manual lymphatic drainage (MLD), a specialised medical massage to soften and drain lymph fluid, and compressive bandaging. Patient compliance with treatments is paramount for their success. Patients are also advised to take regular exercise to control the lymphoedema symptoms. The latter proves a challenge in leg lymphoedema patients because of the morbidity associated with their condition (Bogan et al, 2007). This brings about the risk of a vicious circle where less exercise leads to further worsening of lymphoedema symptoms. Whilst exercise could be of particular benefit for this group of patients' research suggests that around 50% of sedentary adults who start an exercise programme stop within the first 6 months of involvement (Heinen *et al* 2007). Patients may be receptive to this form of exercise especially if they are elderly, frail, have limited mobility, have a fear of falling or are housebound.

This study will apply a StepIt rocker pedal for the first time in patients with leg lymphoedema in addition to the standard care. This is a small pedal device that can be used from a seated position and was first devised to help alleviate the risk of deep vein thrombosis for travellers on long haul flights; a reduction in swelling was demonstrated in people who sat in a sedentary position for lengthy periods (Bergqvist, 2009). Subsequently, the StepIt device has been trialled in a clinic setting in patients with peripheral arterial disease (PAD) and venous leg ulcers, respectively (Tebbutt et al, 2013; Jonker et al, 2019). In the study by Tebbutt et al, encouraging results were obtained - in terms of increase in maximum walking distance for PAD patients who used the StepIt pedal – when a 20-minute exercise regime was prescribed. Jonker et al showed a trend towards improved healing rates of VLUs with the same exercise regime as for PAD patients. The StepIt pedal specifically exercises the calf muscle by performing plantar flexion exercise.

There is evidence that exercise of specifically the calf muscle can improve physiological functioning of said muscle. Exercises such as heel raises, flexion, extension and rotation of the ankles have been shown to increase venous return (Padberg, Johnston & Sisto, 2004, Roaldsen *et al* 2006, Jull *et al* 2009). Up to a third of advanced chronic venous disease conditions present also involve lymphatic pathology, ie phlebolymphoedema, and therefore this group of patients is one of the most prevalent leg lymphoedema cases (Bunke et al, 2009). Goddard and colleagues (2008) showed that oedema could be reversed in patients through micromechanical stimulation of the plantar surface. There is limited empirical evidence that calf muscle exercise by patients themselves can aid in controlling lymphoedema symptoms. However, in a small case series, the combination of compression bandaging and exercise resulted in significant leg volume reduction (Rooney et al, 2018). The 20 minute exercise regime comprised of: walking/marching on the spot, ankle and foot rotation and exion, straightening/bending of leg whilst seated, marching whilst seated. Another study involved leg lymphoedema patients exercising in a pool, five times over three weeks, and a significant reduction in leg volume was achieved (Gianesini et al). An impoved in ankle movement range was also reported, an observation also made in VLU patients who exercise (Davies et al, 2007).

